2. TRIAL OBJECTIVES

2.1. Trial Aim and Hypothesis

FAST-Forward Boost aims to establish a 1-week schedule of SIB radiotherapy as standard of care in patients undergoing radiotherapy for breast cancer +/- lymph nodes with a tumour bed boost. It hypothesises that local recurrence rates at 5-years will be no higher with appropriately dosed 1-week SIB radiotherapy than with 3-week SIB radiotherapy and that this can be achieved without an increase in normal tissue side-effects. A secondary aim is to characterise the pneumonitis rates in the subpopulation of patients who require internal mammary chain (IMC) radiotherapy, hypothesising that these are no higher for IMC radiotherapy delivered in 1-week as in 3-weeks.

2.2. Trial Objectives

Specific objectives are:

1. To establish non-inferiority of 1-week SIB radiotherapy when compared with standard 3-week SIB radiotherapy in terms of local recurrence rates for the treatment of breast cancer requiring radiotherapy with a tumour bed boost.
2. To describe (long-term) clinical outcomes with 1-week SIB radiotherapy compared with 3-week SIB radiotherapy in this patient group
3. To evaluate acute toxicity with 1-week SIB radiotherapy compared with standard 3-week SIB radiotherapy specifically in relation to skin changes and tiredness.
4. To evaluate late effects of 1-week SIB radiotherapy compared with standard 3-week SIB radiotherapy, specifically chronic breast shrinkage, hardness, tenderness and cosmesis.
5. To establish rates of acute lung toxicity (pneumonitis) with 1-week SIB radiotherapy compared with standard 3-week SIB radiotherapy in patients receiving IMC radiotherapy.
6. To establish how early and late side-effects of 1-week versus 3-week SIB radiotherapy impact on patient-reported quality of life and on economic aspects.

3. TRIAL DESIGN

FAST-Forward Boost is a phase III, multi-centre, randomised controlled trial. The patient population is people with a diagnosis of breast cancer treated with breast conserving surgery who are recommended radiotherapy which includes a boost dose to the tumour bed. This includes people who need radiotherapy to nodes (level 1-4 axilla, +/- IMC) in addition to radiotherapy to the breast. A total of 4830 patients will be included.

Patients will be treated using standard radiotherapy to the breast +/- nodes with a SIB to the tumour bed and randomised on a 1:1:1 basis to one of the following schedules:

- Standard radiotherapy to the breast +/- nodes using a schedule of 40Gy/15Fr over 3 weeks with a 48Gy/15Fr simultaneous integrated boost (SIB) of the tumour bed (**Control Group**)
- 26Gy/5Fr over 1 week with a 31Gy/5Fr SIB (**Test Group 1**)
- 26Gy/5Fr over 1 week with a 30Gy/5Fr SIB (**Test Group 2**)

Patients requiring nodal boosts will be eligible for inclusion if they also require a tumour bed boost. The nodal boost will be 48Gy/15Fr if randomised to the control group and 30Gy/5Fr if randomised to either of the test groups.

The trial will provide a robust assessment of the test interventions and, in addition to evaluating tumour recurrences rates (primary endpoint with a non-inferiority hypothesis), will assess toxicity in both the short and longer term (considering both patient and clinician perspectives), as well as health economic consequences and long-term disease outcomes.

The trial includes an Early Side-Effects Sub-Study which will provide an early safety review whilst recruitment is ongoing. The trial will initially open at selected sites who can take part in this sub-study which will include the first 345 patients (approximately) recruited at those sites. Both clinician and patient-reported acute toxicity will be assessed, with a focus on acute skin reactions. In particular, the sub-study is powered to exclude a 10% or greater rate of CTCAE v5.0 skin reactions \geq grade 3 in either of the test arms. Once recruitment to this sub-study is complete then the trial will open to recruitment at further sites.

The trial will also incorporate a recruitment sub-study to assess barriers and facilitators to recruitment in under-served populations (UK only) and two embedded “Studies Within A Trial” (SWATs) considering a new tool for assessing skin toxicity across a range of skin tones, and patient/ healthcare professional views on carbon trade-off decisions in clinical trials. These will be added/activated at a later date.

The trial is 8.5 years in duration including 3.5 years accrual period and 5 years of trial follow-up. Additional follow-up beyond 5 years via routinely collected healthcare datasets (or alternative methods, including ongoing routine data collection at site, where this is not possible) will inform later analyses of long-term outcomes.

This trial has been co-designed with patients and public involvement. Focus groups were held after a national advert (to FAST-Forward trial centres, NIHR People in Research, NIHR BRC Cancer Patient Voice Platform, Independence Cancer Patient Voice, ICR social medial channels and networks linked to co-applicants including Black Women Rising) seeking input from those with lived experience of breast cancer. Over 40 people took part. Patient and Public Involvement (PPI) contributors have been clear that shorter radiotherapy treatment is desirable if it does not compromise the risk of cancer returning. They prioritised local recurrence as the primary endpoint (rather than breast hardness as originally planned) and requested detailed data collection (quantitative & qualitative) about early and late side-effects of SIB, specifically fatigue & QoL, and data that

has not been captured in previous radiotherapy studies (impact on employment/caring, support needed by friends/family during radiotherapy and recovery). The PPI Lead and an additional member will form part of the TMG. Four PPI members reviewed the patient information sheets and informed consent forms.

4. STUDY ENDPOINTS

4.1. Primary Endpoint

The primary endpoint is ipsilateral breast tumour recurrence (IBTR) at 5 years.

4.2. Secondary Endpoints

The secondary endpoints are as follows:

- Patient-reported acute radiotherapy adverse effects, with a focus on skin, breast & oesophageal effects (PRO-CTCAE and trial specific, used in previous trials).
- Patient-reported late effects on quality of life, with a focus on breast symptoms and shoulder/arm functioning, using standard instruments (EORTC QLQ BR-23) and trial specific questionnaires used in previous trials.
- Patient-reported fatigue (EORTC QLQ FA12), health-related quality of life (EORTC QLQ C-30, EQ5D-5L), and body image (Body Image Scale (BIS))
- Clinician-reported acute radiotherapy adverse effects, with a focus on skin, oesophageal (CTCAE v5.0) and lung toxicity (RTOG) and breast oedema (trial specific, used in previous trials).
- Clinician-reported late radiotherapy adverse effects, with a focus on normal tissue effects and cosmesis, assessed with tools developed in previous breast radiotherapy trials and Harvard-Harris scale, and lung toxicity (RTOG).
- Recurrence-free survival, breast cancer-related survival and overall survival using NHS routinely collected data (subject to validation).
- Cost-effectiveness, based on health economic analysis which incorporates data on patient-reported health resource use, out of pocket expenses and health status (EQ5D-5L).

5. PATIENT SELECTION & ELIGIBILITY

5.1. Number of Participants

The aim is to recruit 4830 participants, 1610 into each group of the study.

5.2. Source of Participants

Participants will be recruited from at least 40 participating radiotherapy sites in the UK (initially selected recruiting centres until the early side effects sub-study recruitment is completed) and additional international centre participation from Ireland and France. Sites will be asked to complete an expression of interest initially to assess resources and complete radiotherapy quality assurance prior to opening as a site. Potential participants will be identified in oncology clinics and discussed at Multi-Disciplinary Team (MDT) meetings. ICR-CTSU encourages investigators to consider equality, diversity and inclusion when recruiting participants into its trials. A formal educational package on reducing (sub)conscious biases in trial recruitment will be produced and delivered as part of trial launch and site initiation.

5.3. Inclusion Criteria

1. Age \geq 18 years
2. Histologically confirmed breast cancer (T1-T3, N0-3, M0) (multifocal disease is allowed) requiring a tumour bed boost plus whole breast radiotherapy +/- radiotherapy to nodes* (axilla +/- internal mammary chain) or DCIS (Tis, N0-3, M0) requiring a tumour bed boost according to local centre policy.
3. Treated with breast conservation surgery.
4. Complete microscopic resection (invasive cancer and/or DCIS clear of ink on radial margins or, if at margin, surgeon confirms no further breast tissue to excise)
5. Patient can provide informed consent.

*Axilla levels as per MDM recommendation

NB. Patients with synchronous bilateral breast cancer can be included as long as the disease on at least one side fulfils the inclusion criteria above. Where the patient has synchronous bilateral disease and needs a tumour bed boost on both sides, **both** sides will need to fulfil the inclusion criteria for the patient to be eligible for the trial.

5.4. Exclusion Criteria

1. Treated with ipsilateral mastectomy.
2. Previous radiotherapy to ipsilateral chest area that precludes delivery of a radical dose of adjuvant radiotherapy to the breast with tumour bed boost. *NB For any scenarios where there is overlap with previous radiotherapy, approval must be sought from the FAST-Forward Boost trial team prior to randomisation.*
3. Presence of metastatic disease.
4. Unavailable for any trial-related follow-up.
5. History of malignancy *except* non-melanomatous skin cancer, CIS cervix, previously unirradiated precancerous changes in breast (including ductal carcinoma in-situ and lobular carcinoma in-situ), and non-breast malignancy if curative intent and at least 5 years disease free.
6. Pregnant and/or currently breast feeding. *NB pregnancy status to be verified verbally with each patient as part of standard radiotherapy consent undertaken prior to randomisation of an individual into the trial*
7. Being treated with proton beam therapy

6. SCREENING

6.1. Screening Log

All participating sites will be required to keep a log of all patients with breast cancer that are potentially eligible for this study.

The information collected on the log will include:

- Date patient identified as potentially eligible.
- Screening outcome (patient approached/accepted participation/declined participation)
- Nodal status
- Reasons for not approaching / declining participation (patient ineligible / if available)
- Trial ID (if applicable)

This information will be used by the TMG to monitor recruitment activity. No patient identifiable data will be sent to ICR-CTSU at this stage.

6.2. Procedure for Receiving Informed Consent

The Principal Investigator (or designated individual) must ensure that each trial patient is fully informed about the nature and objectives of the trial and possible risks associated with participation. Participants should be given the current ethics approved FAST-Forward Boost patient information sheet for their consideration. Patients should only be asked to consent to the study after they have had sufficient time (usually at least 24 hours but at least overnight) to consider the trial, and the opportunity to ask any further questions. Initially selected sites who will participate in the early side-effects sub-study will open to FAST-Forward Boost trial and should ensure that the FAST-Forward Boost patient information sheet including early side-effects sub-study is given. Whilst the sub-study is ongoing, patients must take part in the early side-effects sub-study in order to participate in FAST-Forward Boost. Once this sub-study is complete, then the FAST-Forward Boost patient information sheet should be given. The patient information sheets are also available in large font for patients who would benefit from this.

Remote consent is permitted provided the following steps are taken:

- A member of the research team should contact the patient to introduce the trial and to organise a telephone appointment with an Investigator in order for the Investigator to discuss the trial with the patient in detail.
- A copy of the ethics approved PIS and ICF should be sent to the patient by email or post ahead of the scheduled appointment so that the patient has sufficient time to review the trial information. (If sending by post, two copies should be sent – one for the patient to retain and one to return to the site).
- During the telephone appointment the Investigator should complete the informed consent process remotely, discussing the study and ensuring that the patient is fully informed.
- If the patient agrees to consent the Investigator should ask the patient to initial the sections of the ICF and sign and date two copies. They should ask the patient to email/post one copy back to the site as soon as possible.
- The Investigator should record the date of verbal consent in the patient's clinical notes and confirm to the patient that this consent has been noted.
- The ICF should be received from the patient within a week of consent. Sites should follow up with patients on any consent forms not received until they have been received, signed and filed.
- On receipt of the signed copy of the ICF from the patient, the consenting Investigator should add their signature and date of signing and place in the patient file.
- A completed copy should be emailed/posted to the patient for their records.

Additionally, an optional short summary information leaflet is available to provide initial information to patients, as part of a layered approach, if suitable. However, all participants will need to be given the full Patient Information Sheet as a basis for written informed consent.

No protocol required assessments should be conducted until the FAST-Forward Boost consent form has been signed and dated by both the patient and the Investigator unless the assessments are performed routinely as part of standard patient care.

Confirmation of the patient's consent and the informed consent process must be documented in the patient's medical notes. A copy of the signed consent form should be provided to the patient and the original retained in the investigator site file, which must be available for verification by ICR-CTSU study staff or for regulatory inspection at any time. GCP-compliant electronic consent forms may be used where available.

6.3. Participation in other clinical trials

Patients who fulfil the eligibility criteria will be given the opportunity to participate in FAST-Forward Boost if they have participated in other clinical trials prior to recruitment assuming there are no fundamental incompatibilities between the trials.

Note that, at this time, concurrent participation in both FAST-Forward Boost and PARABLE (ISRCTN14220944) is not possible. Where a patient is potentially eligible for both trials, PARABLE should be discussed/offered in the first instance at centres recruiting to both trials. FAST-Forward Boost should only be considered once it has been decided that the patient will not enrol in PARABLE.

Patients recruited to ATNEC (ISCRTN36585784) can also be recruited to FAST-Forward Boost if they meet the eligibility criteria.

In case of queries regarding participation in other trials, please contact the trials team for advice.

7. TRIAL ENTRY/RANDOMISATION

Pre-treatment assessments must be completed after consent if not performed as standard of care but before first radiotherapy treatment.

Trial entry and treatment allocation (randomisation) will be done by site staff on the FAST-Forward Boost trial database. Once a patient has provided consent, they can be added to the database, which will generate the patient's unique trial number (Trial ID). Treatment allocation (randomisation) should take place as soon as possible after the patient has given trial consent and been added to the database (but ideally after completion of the baseline PRO booklets).

The following information must be completed on the database before the patient can be randomised:

- Name of randomising and treating hospital, consultant.
- Confirmation that the patient has given written informed consent for trial participation and for any sub-studies.
- Patient preference of whether they would like to receive questionnaires by paper or electronic method (all patients).
- Confirmation that the patient has been provided the pre-treatment PRO booklet (subject to consent).
- Confirmation that the investigator has confirmed in writing that all of the eligibility criteria were met. We recommend (but do not mandate) the paper eligibility checklist is used for this.
- Patient's full name*, hospital number*, date of birth*, address* and postcode*, NHS/CHI number*, and email address (if patient would like to complete PRO electronically, once available).
- Type of surgery.
- Whether radiotherapy to regional lymph nodes is required; if yes: whether this includes IMC.
- Estimated radiotherapy start date.
- In which breast/side disease was diagnosed; if bilateral, which side(s) require(s) a boost.
- Whether patient is taking part in early side-effects sub-study (until sub-study recruitment is complete).

- Whether patient has consented to optional aspects of the study.

* Not required for international participants. For international participants, only initials and partial date of birth will be collected.

Once this information has been entered, the randomisation form will become available, and the patient can be randomised by completing the questions on the form. The system will confirm the patient's treatment allocation. As this is an electronic system sites will have access to this at all times, but the ICR-CTSU FAST-Forward Boost trial team will only be available between 09.00-17:00 (UK time) Monday to Friday excluding bank holidays and closure periods.

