8.2. Administration of (e)PRO booklets

All patients who have consented to complete PRO questionnaires will be asked to complete questionnaires at pre-treatment, then from the start of radiotherapy at weeks 1, 2, 3 and 5, 3 months and annually from 1-5 years.

Patients in the early side-effects sub-study will additionally be asked to complete questionnaires at weeks 4, 6 and 7.

It is anticipated that the option of electronic completion (ePRO) will become available whilst the trial is recruiting. Patients will be asked at randomisation whether they prefer electronic or paper questionnaire completion. The FAST-Forward Boost trials office will inform the sites and recruited patients who prefer electronic PRO completion when it is available.

Paper PRO completion

Pre-treatment (baseline) questionnaires will be in a booklet and handed out in the clinical centre by a member of staff. Patients will be asked to complete the questionnaires after a full explanation of the study and after giving informed consent. They should be completed before first radiotherapy treatment and, ideally, before patient is informed of treatment allocation, to avoid the possibility of bias. It is the responsibility of the clinical centre to ensure the completed pre-treatment booklet is sent to the trials office.

Patients will be asked to complete subsequent questionnaires at the timepoints described above. The booklet containing questionnaires for weeks 1, 2, 3 and 5 will be given to the patient at the start of radiotherapy. Sites should remind patients to complete their trial questionnaires on a regular basis. For UK patients all other booklets will be posted to the patient's home from the trials office. Patients will be sent a pre-paid envelope to return each completed booklet to the FAST-Forward Boost trials office (UK only). For international sites all booklets will be administered by the site or national coordinating group.

Early side-effects sub-study

Patients taking part in the early side-effects sub-study will be given a booklet containing questionnaires for weeks 1-7 from the start of radiotherapy and be asked to return the completed booklet to the trials office in

the pre-paid envelope. Sites should regularly remind patients to complete their trial questionnaires on a weekly basis.

Questionnaires for later timepoints will be posted directly to the patient from the trials office.

Electronic PRO completion (ePRO)

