10.2. Treatment Allocation

All trial participants will receive radiotherapy.

Participants will be allocated between the three groups – control, test group 1 and test group 2 - on a 1:1:1 basis (open-label). Allocation will be by computer generated random permuted blocks. Randomisation will be stratified by:

- breast surgery type (breast conservation surgery (including mammoplasty) or breast conservation surgery with perforator flap reconstruction)
- need for nodal radiotherapy (none, nodes not including IMC or nodes including IMC)
- treating centre.

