The primary endpoint will be presented by trial arm using Kaplan-Meier curves; estimated 5-year event rates will be given along with 95% confidence intervals. The treatment effect from each pairwise comparison will be presented as an absolute difference, by applying the hazard ratio (and corresponding 95% confidence interval) to the control group 5-year event-free estimate. This will be the primary assessment of non-inferiority (whether or not the upper limit of the confidence interval exceeds 2%). Additionally, the hazard ratio will be used to present treatment effect on a relative scale, presented with a 95% confidence interval. Hazard ratios will be derived from Cox proportional hazard regression models. The primary analysis will be unadjusted, but estimates will also be presented after adjustment for factors used in the randomisation algorithm and other important prognostic factors (which will be pre-specified in the analysis plan). As noted above, a sensitivity analysis based on a per protocol population will also be reported. The proportional hazards assumption will be checked and, if violated, appropriate alternative methods will be applied.

Analysis of secondary endpoints

PRO questionnaires will be scored using published manuals, including methods for handling missing data. Analyses of both patient-reported and clinician-reported toxicity data will follow methods established in previous breast radiotherapy trials(6, 10, 16, 39, 40) (11) and will account for multiple testing by adjustment of significance levels. Frequencies of early and late toxicities will be summarised at each time point/period and compared between treatment groups using chi-squared test or Fisher's exact test as appropriate. Where appropriate, longitudinal models (e.g. generalised estimating equations) including all assessments over follow-up, and survival analyses of time to first moderate/marked adverse effect will be carried out with comparisons between treatment groups, adjusting for balancing and other factors (for example, pre-treatment HADS score) where relevant. Event rates at key time points will be reported with 95% confidence intervals. For the analysis of late radiation effects on normal tissues the two test groups will be compared to estimate by interpolation the 5Fr schedule equivalent to control in terms of adverse effects.

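### Randomisation requires only that the baseline PRO booklet has been provided, so baseline patient-reported scores can be recorded after an open-label allocation is known

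*Protocol*

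**What the plan says.** The trial allocates patients on a "1:1:1 basis (open-label") (section 10.2).

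Section 7 sets the conditions for randomisation. The questionnaire item is "Confirmation that the patient has been provided the pre-treatment PRO booklet (subject to consent"). When the listed items are in, "Once this information has been entered, the randomisation form will become available", and the system then gives the allocation. The same section asks for randomisation as soon as possible after consent, "but ideally after completion of the baseline PRO booklets". The firm deadline is a different one: "Pre-treatment assessments must be completed after consent if not performed as standard of care but before first radiotherapy treatment".

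Section 8.2 says of the paper baseline questionnaires: "They should be completed before first radiotherapy treatment and, ideally, before patient is informed of treatment allocation, to avoid the possibility of bias". The note at the end of section 8.4 repeats the preference. Section 8.12 asks for radiotherapy to start ideally within 4 weeks of randomisation.

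Two uses of the baseline scores are stated. Section 10.4 describes longitudinal and time-to-event models for toxicity, "adjusting for balancing and other factors (for example, pre-treatment HADS score) where relevant". Appendix A3 says that EQ-5D-5L scores will be compared over time and between the 5-fraction and 15-fraction groups, to inform quality-adjusted survival.

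**The concern.** A baseline score can be treated as free of treatment influence only if it was recorded before the patient could react to the allocation. Here the patient learns whether treatment will last 1 week or 3 weeks. That knowledge could plausibly change answers on anxiety, which is measured by HADS and is one of the five EQ-5D-5L dimensions.

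A score collected after that moment is a post-randomisation variable, even if the protocol calls it pre-treatment. Adjusting for it can move the between-arm estimate. A between-arm comparison over time that starts from it may start from arms that already differ. The protocol names this risk itself, but does not enforce the preferred order at the step where it controls entry.

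**Working it through.** The protocol has no figure to reproduce. The check is whether a fully compliant site can produce a baseline score after allocation, and where such a score would be used.

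**Can it happen?**

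| Step | Rule | Binding? |
|---|---|---|
| Booklet handed over before randomisation | Section 7, database item | Yes |
| Booklet completed before randomisation | Section 7 | Preference |
| Booklet completed before the patient knows the arm | Sections 8.2 and 8.4 | Preference |
| Baseline assessments done before first radiotherapy | Sections 7 and 8.4 | Yes |
| First fraction within 4 weeks of randomisation | Section 8.12 | Preference |

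One permitted sequence is consent, booklet handed over, database items entered, allocation issued, patient told, booklet completed, first fraction. No binding rule is broken. The interval between allocation and completion can run to the first fraction, which ideally means up to 4 weeks.

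Ordinary practice makes this sequence plausible. Consent may be taken by telephone (section 6.2), paper baseline booklets are handed out at the centre (section 8.2), and electronic completion is described as still to come (section 8.2). Sites must see that the completed booklet reaches the trials office, but nothing ties this to randomisation.

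**Where would such scores be used?**

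- HADS is the only baseline score named as a covariate, and only as an example. It is collected only in the early side-effects sub-study (section 8.4, Appendix A2): 345 / 4830 = 0.071, about 7% of the trial.
- EQ-5D-5L is in the pre-treatment booklet of every participant who consents to PROs (section 8.4), and its comparison between the fractionation groups is stated in Appendix A3.

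**Where would they not be used?**

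- The primary analysis of ipsilateral breast tumour recurrence is unadjusted (section 10.4).
- The sub-study's primary endpoint is a clinician-reported CTCAE rate in each test group, analysed without comparison to control (section 10.1).
- Toxicity frequencies at each time point are compared by chi-squared or Fisher's exact test (section 10.4), which uses no baseline value.

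**How large could the effect be?** In a linear model adjusted for the baseline score, the between-arm estimate moves by about

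p × d × b,

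where p is the proportion completing after the allocation is known, d is the between-arm difference in the shift that this knowledge causes among them, and b is the slope of outcome on baseline. The protocol gives none of the three. If p or d is zero, there is no bias. If all three are non-zero, the bias does not shrink as the sample grows.

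**The case against.** The strongest reply is that the protocol has seen the problem. It states the preferred order three times and gives the reason once. The soft wording can be read as a deliberate trade-off, because randomisation and radiotherapy are both wanted as soon as possible and a paper booklet can be slow to come back. A second reply is that the choice of covariates and the handling of late baselines belong to the analysis plan, which is not shown. It also cannot be said that completion dates go unrecorded, since the booklets and eCRFs are not shown either.

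Much of this stands. It limits the point but does not remove it. An analysis plan can exclude a late baseline but cannot recover the one that should have been taken, so the order has to be secured at trial entry. The trade-off can be kept by a database item that accepts a recorded reason for non-completion.

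A reader might infer more than the text supports:

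- *That baseline scores in general are covariates.* Only HADS is named, as an example and where relevant.
- *That change from baseline is biased.* No such analysis is stated.
- *That the baseline clinician breast assessment raises the same problem.* It has the same deadline, but its use as a covariate is not stated.
- *That the choice between the 30 Gy and 31 Gy schedules is at risk.* The mechanism is a reaction to 1 week versus 3 weeks. Both test schedules take 1 week, so it gives no reason for baseline answers to differ between them.
- *That participants are known to favour the shorter arm.* Section 3 reports the view of patient and public contributors, and it was conditional on recurrence risk not being compromised.

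**Conclusion.** The point holds, with a narrow scope. The condition for randomisation is that the booklet was provided, and nothing binding prevents completion after an open-label allocation is known. What is exposed is the set of secondary control versus 1-week comparisons that use baseline PROs: HADS-adjusted models in the sub-study of about 345 patients, and the EQ-5D-5L comparison. The documents do not show any effect on the primary recurrence analysis, the sub-study's CTCAE endpoint or the choice between test schedules.

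The size of the bias is unknown. It rests on two assumptions that the protocol can neither confirm nor exclude: that some patients complete the booklet after learning their arm, and that the knowledge shifts answers differently between control and 1-week patients. The case for acting is that the change is cheap and that a baseline taken too late cannot be retaken.

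**What to change.** 1. In section 7, change the database item from *has been provided* to *has completed* the pre-treatment PRO booklet, for patients who consented to PROs. Add *declined or unable* as a recorded alternative, so that nobody is blocked from randomisation.
2. Align sections 8.2 and 8.4 with this, so that completion before the allocation is known becomes the rule and the recorded alternative the exception.
3. Record the completion date relative to allocation, if the booklet or eCRF does not already do so.
4. In analyses that use a baseline PRO, add a sensitivity analysis that excludes baselines completed after the allocation was known.

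The cost is one changed database field, short wording changes in three sections and one added analysis. Some patients may be randomised slightly later, mainly those using paper booklets or consenting remotely. PROs stay optional in the main trial, because the item applies only to those who consented to them.
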